Implementing nature-based VR allows patients to feel present as if they were genuinely standing in outdoor environments without the challenges of leaving their homes.⁹ Personalizing these VR experiences allows patients to revisit familiar and non-threatening spaces where memorable experiences occurred.^{10,11} Implementing such a personalized, technologically-advanced intervention among patients enrolled in hospice is expected to significantly mitigate stressors associated with serious illness and EOL events by bringing joy and closure at the end of their lives.¹²

Patients are not the only individuals in the hospice setting who can benefit from nature-based VR experiences. Informal caregivers, such as a spouse, partner, or friend, play crucial roles in hospice patients' physical, emotional, and practical care. On average, these caregivers deliver an estimated 66 hours per week of care and are intimately involved in the EOL phases.¹³ Providing this amount of care requires significant physical and emotional sacrifices. Caregivers' own health often deteriorates as the burden and strain of caregiving increases.¹⁴ The psychological distress of the patient-caregiver dyad is interconnected and highlights the interdependence and responsiveness to distress as a unit.¹⁵ While caregivers survive beyond the patient, reducing their physical and psychological impact offers long-term benefits in their well-being and bereavement process.¹⁶ What is currently missing from hospice care services and this public health issue is a strategy to help reduce burnout and the impact of caregiving on informal caregivers. Therefore, the use of simultaneous personalized nature-based VR, or Tandem VR, experiences may provide the needed strategy for the well-being of the dyad by allowing them to engage in meaningful experiences simultaneously.

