- Eligible participants will meet with the Research Recruiters and baseline data will be collected including demographics. Also, participants will complete Wisconsin Brief Pain Questionnaire (WBQP), Collett-Lester Fear of Death (FOD) scale, and McGill Quality of Life (QOL) scale directly before and after the intervention.
- Research recruiters will meet with participants in the home setting to assist dyads and implement the Tandem VR intervention.
- Upon completion of the intervention, Research Recruiters will collect the Tandem VR equipment and readminister the WBQP, FOD, QOL instruments, and semi-structured interviews.
- Consent from dyads will have been obtained by the Research Recruiters to participate in the Patient Advisory Council (PAC) to work with the researchers on understanding the experience.

Intervention

All procedures completed below will be done on one home visit.

The Tandem VR intervention will be carried out in the patient-caregiver dyad's home setting with the Research Recruiters implementing the experience. Each member of the dyad will initially complete the McGill Quality of Life Questionnaire-E (MQOL-E), Wisconsin Brief Pain Questionnaire (BPQ), and Collet-Lester Fear of Death (FOD) Scale prior to beginning the Tandem VR experience through an electronic medium.

Following completion of the pre-intervention forms, the dyads will be assisted by the Research Recruiter to don the VR HMD. The Research Recruiter will ensure safety for both participants while using the devices. The Research Recruiter will then initiate the Tandem VR experience using the iPad device to synchronize the nature-based scene for viewing. The duration of the experience will be 5-15 minutes.

Upon completion of the Tandem VR intervention, the HMD devices will be removed from the dyad participants. They will then complete the three instruments of the MQOL-E, BPQ, and FOD. Following the completion of the post-intervention documents, the Research Recruiter will conduct the semi-structured interview with the participants. Each participant will be asked the following questions to reflect on their experience:

- Tell us about your experience in Tandem VR?
- What was it like being together in the Tandem VR experience?
- Was there anything about the Tandem VR experience that helped you?
- Was there anything about the Tandem VR experience you feel could be improved?

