- Were there any unusual sensations such as dizziness, lightheadedness, or disorientation while you were in the Tandem VR experience? If so, please explain.

These procedures will be carried out with each dyad for a duration of 8-16 weeks to ensure enough participation in the study. Research Recruiters will also identify participant dyads that can participate in the PAC to discuss the experience with the primary research team.

At this point the study will be completed for the dyads.

The study will recruit 20+ patient-caregiver dyads from Prisma Health Hospice of the Foothills. The participants will be enrolled in the study for 1 intervention with Tandem VR. Each dyad will receive \$20 for participating in the study (a \$10 gift card to the patient and \$10 gift card to the caregiver).

Cleaning and Disinfection of VR -Head Mounted Display (VR- HMD)

As part of a clinical study, virtual reality headsets will need to be reused between patients. At the end of the intervention the VR- HMD will be disinfected. Infection control measures include:

- Hand hygiene will be performed prior to cleaning and disinfection of HMD.
- Headsets that are disinfected will be handled with clean hands to prevent contamination.
- Participants will be instructed to not use headsets if there is a break in their integrity or have visible soiling.

Cleaning of HMD:

Use manufacturer's approved (VRCOVER antibacterial wipes) wipes for removal of all visible bioburden from headset and controller for disinfection.

Disinfection of HMD:

Follow cleaning instructions using disinfection wipes.

The above cleaning protocol has been approved by Prisma Health Infection Prevention.

Participants will continue to follow-up as normal with their physicians at Prisma Health Hospice of the Foothills.

1. Study Timelines

Tandem VR: Synchronized Nature-Based Experiences in Virtual Reality for Hospice Patients and their Caregivers

Table 1 Schedule of Assessments (Study Calendar)

Procedures	Pre-Intervention	Post-Intervention	PAC Meeting (Week 8)
Informed consent	X		
Inclusion/exclusion criteria	X		
Demographics	X		
Cognitive Assessment	X		
McGill Quality of Life Questionnaire-E (MQOL-E)	X	X	
Wisconsin Brief Pain Questionnaire (BPQ)	X	X	
Collett-Lester Fear of Death (FOD) Scale	X	X	
Semi-Structure Questions		X	
Dyads for PAC			X

Timeline of Study

*N_{total} ≥ 20 Patient-Caregiver Dyads

Inclusion Criteria:

- Ability to speaking English

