The EXCEL spreadsheet below contains the specific patient-level variable listing that will be collected by the PRR/PRT. The PRR/PRT will establish the guideline for managing confidentiality of the single data file containing the participant names and study ID numbers. Time Frame: The PRR/PRT will collect these data points prior to the participant's completion of the research intervention and following the intervention. These data will allow the researchers to determine the effectiveness of the intervention.

EXCEL Spreadsheet. Patient level data retrieved from EHR by PRR/PRT

Patient's Information. Each patient's name will be transposed into a unique (random) study identification number by the PRR/PRT: year of birth, gender, racial group, ethnicity, primary diagnosis for enrollment into hospice, length of time in hospice care services.

Participant-level data. When participants give consent and are enrolled in the study, each will be assigned a unique (random) study identification number by the PRR/PRT. This ID number will be associated with all participant data that are collected, entered, and analyzed for the study. The link between participants' names and study ID numbers will be kept in a separate electronic file on the computer of the PRR/PRT PI on a password protected computer that is kept in locked office, ensuring that all data prepared for analysis are de-identified. Directly identifying information will never be maintained in the same files. All paper data (pre- post- intervention) will be stored in locked file cabinet that will be accessible only to research staff at the Prisma Health Hospice of the Foothills site. The paper data will only be labeled with the participant's study ID. During the active project period (while data are being collected, coded, and analyzed), data from participants will be entered into the data spreadsheet (included for review) by the PRR/PRT into the Clemson University's secure BOX storage (box.clemson.edu), which is a highly secure online file-sharing system.

Participants' study ID numbers will be associated with the data entered into BOX. Data will be downloaded from BOX for analysis onto password protected computers and saved only on secure Clemson University servers.

Patient-level data retrieved from EHR by the Tandem VR Team

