Data from this study will be stored in HIPAA compliant Box software. The Co-PIs, Co-Is, and the research assistants will have password protected access to the Box. All the information will be stored in an encrypted database. Electronic communication with outside collaborators will involve only unidentifiable information. Only the primary investigators and members of the research team that will contact the participants will have access to information linked to participant identifiers. Long-term plans for archiving data, samples, and other research products, and preservation of access will be undertaken by [name] and [name], RN, CHSE. The Co-PIs and Co-Is will maintain their parts of the data on the Box platform. The data will be retained at least three years after the conclusion of the study. Other electronic backup media and surveys will also be stored to ensure long-term availability of data. Should the Co-PI leave Prisma Health prior to completing the research, the data will be moved either to the relocating Co-PI's new institution, the Co-I's location, and/or to a site maintained by another member of the research community involved with the project. Data from this study will be retained to assist in development of future studies with larger patient populations, multi-site studies and also to aid in application for extramural funding.

7. Statistical Analysis

Differences in outcomes between pre and post intervention data will be statistically tested to determine if Tandem VR impacted primary outcomes. Independent sample t-tests will compare outcomes and changes in symptoms (i.e., pain). We will also triangulate quantitative and qualitative data outcomes with adjustments for sociodemographic characteristics to understand experiences for both the patient and informal caregiver following conclusion of the intervention.

V. ETHICAL CONSIDERATIONS

A. RISKS AND POTENTIAL BENEFITS TO PARTICIPANTS

1. Risks to Participants

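### The protocol names only independent-samples t-tests for a before-after comparison of the same people, and the SAP does not repair this

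*Protocol*

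**What the plan says.** Protocol section IV.E.7 (Statistical Analysis) opens with the aim: "Differences in outcomes between pre and post intervention data will be statistically tested to determine if Tandem VR impacted primary outcomes". The next sentence names the method: "Independent sample t-tests will compare outcomes and changes in symptoms (i.e., pain". No other test is named in either document.

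The data come from one group. Under section IV.E (Intervention), before the session, "Each member of the dyad will initially complete the McGill Quality of Life Questionnaire-E (MQOL-E", together with the pain and fear-of-death scales. After it, "They will then complete the three instruments of the MQOL-E, BPQ, and FOD". The schedule of assessments (Table 1) shows the same pre and post pattern. There is one session per person: "The participants will be enrolled in the study for 1 intervention with Tandem VR". No control arm is described.

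On the link between patient and caregiver, the Background (II.A) says: "The psychological distress of the patient-caregiver dyad is interconnected and highlights the interdependence and responsiveness to distress as a unit".

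The SAP (Primary outcomes) lists the same three scales and plans means and standard deviations for them. It does not say whether these are for each time point or for the within-person change. Pain and fear of death are worded as a change; the quality-of-life scale is not. The fourth primary outcome is qualitative, has a thematic analysis, and is not at issue here.

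**The concern.** An independent-samples t-test assumes that the two sets of scores come from unrelated people. Here the pre and post scores come from the same people, minutes apart, so the assumption fails by design. The test compares the mean shift with the full spread between people, although that spread cancels when each person is compared with themselves.

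At stake is the quantitative answer on all three primary scales. The target is 20 or more dyads, the Sample Size entry reads n/a, and the results are meant to support an application for external funding (III.A). A real moderate improvement could be reported as no effect, or with an interval too wide to plan from.

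**Working it through.** The plan states no power, alpha, effect size or correlation, so there is no figure of its own to reproduce.

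**Inputs**
- From the protocol: at least 20 dyads, so n = 20 pairs in one role; one group; one pre and one post score per person on each scale.
- Assumed: two-sided alpha 0.05, equal pre and post SDs, normal scores, pre-post correlation ρ from 0.3 to 0.8, and a true shift d of 0, 0.5, 0.8 or 1.0 SD.

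**Standard error of the mean change, in SD units**
- Unpaired: √(2/n) = √(2/20) = 0.316.
- Paired: √(2(1−ρ)/n). At ρ = 0.5 this is √(1/20) = 0.224.
- Ratio: 1/√(1−ρ). At ρ = 0.5 this is 1.41.

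**95% interval half-width**
- Unpaired: t(38) × 0.316 = 2.024 × 0.316 = 0.64 SD.
- Paired at ρ = 0.5: t(19) × 0.224 = 2.093 × 0.224 = 0.47 SD.

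**Power**
- Paired: noncentral t with 19 degrees of freedom and noncentrality d√n / √(2(1−ρ)). For d = 0.5 and ρ = 0.5 this is 0.5 × 4.472 / 1 = 2.236, which gives 56%.
- Unpaired: simulated on the same correlated pairs, with the usual 38 degrees of freedom.

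| ρ | SE ratio | Half-width, unpaired / paired (SD) | True size of nominal 5% unpaired test | Power at 0.5 SD, unpaired / paired |
|---|---|---|---|---|
| 0.3 | 1.20 | 0.64 / 0.55 | 2.1% | 31% / 43% |
| 0.5 | 1.41 | 0.64 / 0.47 | 0.7% | 29% / 56% |
| 0.7 | 1.83 | 0.64 / 0.36 | 0.1% | 25% / 78% |
| 0.8 | 2.24 | 0.64 / 0.30 | 0.01% | 22% / 92% |

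For larger shifts the gap closes. At 0.8 SD, power is 72% against 82% (ρ = 0.3) and 76% against 92% (ρ = 0.5). At 1.0 SD it is 91% against 95% and 94% against 99%.

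**A trap in the repair.** Suppose the 20 patients and 20 caregivers were pooled and their 40 change scores treated as independent. The nominal 5% test would then reject a true null about 7%, 10% and 12% of the time, at within-dyad correlations of the changes of 0.2, 0.4 and 0.6 (assumed; simulated). Using the mean change of each dyad, the rate is 5%. This describes a possible wrong fix, not the present plan.

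**The case against.** The strongest reply is that the two sentences in IV.E.7 are separate: the first promises a pre-post test without a method, and the second compares changes between two groups, perhaps patients and caregivers, whom the paragraph mentions next. This is a possible reading, and on it the power figures above do not describe the planned test. It does not rescue the plan. Patients and caregivers are matched in dyads, and the Background calls their distress interdependent, so independence fails there too. The promised pre-post test would then have no method at all.

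A comparison of changes between demographic subgroups would have independent samples. The protocol mentions sociodemographic adjustment in IV.E.7 and secondary use of age, sex and race in IV.E.4. It defines no subgroup t-test, however, and such a test would not answer the pre-post question.

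A third reply is that the SAP settles for description, which suits a small single-group study. If only the SAP is followed, no wrong test is run. But the SAP does not say that testing is dropped, the protocol sentence still stands, and neither document says which governs.

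Finally, the error is conservative, and a paired analysis stays possible after collection because the raw data are kept under a study ID. That is true, and it limits the harm. It does not make the named test suitable.

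**Conclusion.** The concern holds. The only test named for the three quantitative primary scales does not fit a design in which the same people are measured twice, and the SAP does not clearly replace it.

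If the unpaired test is used for the pre-post question, with 20 pairs and equal SDs, standard errors are 1.20 to 2.24 times too large for ρ from 0.3 to 0.8. Power for a 0.5 SD shift is 22% to 31%, where a paired test would have 43% to 92%. These figures rest on assumed correlations and shifts. With positive correlation the false-positive rate falls rather than rises, and for shifts near 1 SD the loss is only about 4 to 5 percentage points at ρ of 0.3 to 0.5. Because the defect lies in the only test offered for the primary question, it should be corrected before analysis.

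**What to change.** In protocol section IV.E.7, replace the sentence on independent-samples t-tests with wording such as:

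> For each of MQOL-E, BPQ and FOD, post minus pre will be computed per participant and tested with a paired t-test, with a Wilcoxon signed-rank test as a check, separately for patients and for caregivers. The two roles will not be pooled as independent observations; any combined analysis will use dyad means or a model with a dyad term. Any patient-caregiver comparison will be paired by dyad.

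A mixed model with person and dyad effects would also suit the design.

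In the SAP, state for all three scales and for each role the mean and SD at each time point, and the mean and SD of the within-person change with its 95% confidence interval. Say whether the protocol or the SAP governs. If testing is to be dropped, withdraw the protocol sentence. Report the result as pre-post change, since a paired test does not stand in for a control group.

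The cost is wording in two documents. Pre and post scores can already be linked, because section IV.E.5 says of the study number: "This ID number will be associated with all participant data that are collected, entered, and analyzed for the study". That section gives a random number to each person ("each will be assigned a unique (random) study identification number by the PRR/PRT") and mentions no dyad number. The spreadsheet is not visible, so add a dyad number if it lacks one. Participants provide nothing further.

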Informal, unpaid caregivers (CGs) are defined as a relative, possibly a spouse or partner, friend or neighbor, who supports the broad range of needs of the patient (Jacobs et al., 2022). The care may often include financial and legal support (Li et al., 2018). Nearly 66 million Americans serve as CGs (National Alliance for Caregiving & American Association of Retired Persons, 2015).

Providing the necessary care creates financial issues and social isolation (Faronbi, Faronbi, Ayamolowo, & Olaogun, 2019). With CGs being the primary source of care, the annual estimated loss of income is \$522 million, and replacing these with unskilled paid care at minimum wage would cost \$221 billion a year (Chari, Engberg, Ray, & Mehrotra, 2015). As a dyad, they may be bound to the home for extended periods without reprieve from outside sources. As social isolation continues, physical and psychological issues become exacerbated (Donovan & Blazer, 2020).

VR is a cutting-edge technology increasingly used by palliative care and hospice organizations worldwide to help bring meaning, joy, healing, and closure to many patients at the end of their lives (Carmont & McIlpatrick, 2022). This technology includes a VR headset that patients wear over their eyes, providing a complete, 360-degree, immersive virtual experience. An example of the benefit of this technology is a patient who has dreamed of visiting another country but cannot leave their bed due to sickness, frailty, and weakness. An immersive VR experience brings distance

areas to the patient at the bedside and helps them complete unreachable locations while providing existential closure.

The experience can also be shared through Tandem VR. In this environment, not only does the patient get to visit another place where they have never been, the caregiver can go with them. The dyad is joined via two headsets controlled by a central laptop or tablet device to project the same videos and imagery into the experience simultaneously. The dyad can communicate openly to each other, especially their emotions from the interaction. Personalizing the experience for the dyad also helps them to see a place that feels authentic to them, allowing them to feel a part of the environment without having to navigate the challenges of travel. The novel concept of Tandem VR provides a strategy to develop person-centered care simultaneously with the caregiver to relive or create meaningful experiences.

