- Have a condition that interferes with VR usage, including but not limited to seizures, facial injury precluding safe placement of headset.
- Have a prognosis of hours or actively dying at the time enrollment.
- Patients with motion sickness
- Patients with claustrophobia
- Patients with visual and hearing impairment
- Patients with inability to speak English.

3. Sample Size

n/a

4. Local Number of Participants

The study will recruit 20+ patient and caregiver dyads from Prisma Health Hospice of the Foothills

5. Study-Wide Number of Participants

This is a multi-site study, and we expect to recruit a total of 20+ patient-caregiver dyads from Prisma Health Hospice of the Foothills across the upstate of South Carolina through hospice and bereavement services in Oconee, Pickens, Greenville, and Anderson counties.

6. Recruitment Methods

Prisma Health Institutional Review Board approvals will be obtained for the study.

Participants will be primarily recruited using flyers and word-of-mouth. Research Recruiters (n=10) will be CITI trained, affiliated with, and working alongside with Prisma Health Hospice of the Foothills staff. Recruiters will assist with consenting dyads, launching the intervention, data collection, and offering expert insights on the use of the intervention as a non-pharmacological modality. Ongoing dialogue between the social workers and the research team will allow for continuous improvement in the intervention delivery and offer data on the acceptance of the intervention for hospice patients and caregivers. All information will be explained in a nontechnical fashion and ample time will be available for the participants to ask any questions. This study will recruit a total of 20+ patient-caregiver dyads who will then be screened using the inclusion and exclusion criterion to ensure participant eligibility.

Flyers about the study, word-of-mouth from Research Recruiters.

E. SPECIFICS OF STUDY PROCEDURES

Screening and Pre-intervention

- Enrolled participants will be consented to per approved Prisma Health consent.
- Consented participants will be screened by the research assistant to ensure eligibility of participants, based on inclusion/ exclusion criterion and will complete the Tandem VR Intake form.

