**For all three quantitative measures means and standard deviations will be calculated to summarise the results.**

4. Open-ended questions will be asked to determine the perceived benefit and value of the Tandem VR post-intervention with patient-caregiver dyads.

**Themes will be derived from the responses provided by the dyads, providing rich insights on the intervention to inform the researchers of individual experiences.**

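### The only named test assumes independent observations, and neither document sets a unit of analysis that respects the patient-caregiver pair; any result that pools or compares the two roles would have the wrong precision.

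*Protocol*

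**What the plan says.** Protocol IV.E.7 (Statistical Analysis) opens with a pre/post contrast: "Differences in outcomes between pre and post intervention data will be statistically tested to determine if Tandem VR impacted primary outcomes". It then names the method: "Independent sample t-tests will compare outcomes and changes in symptoms (i.e., pain"). The one adjustment mentioned is part of combining quantitative and qualitative findings: "adjustments for sociodemographic characteristics to understand experiences for both the patient and informal caregiver". The SAP, under Primary outcomes, says "For all three quantitative measures means and standard deviations will be calculated to summarise the results" and names no test or interval.

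The design links the two members of each pair:

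- **Shared exposure** (III.A): "The dyad is joined via two headsets controlled by a central laptop or tablet device to project the same videos and imagery".
- **Both members measured** (IV.E, Intervention): "Each member of the dyad will initially complete the McGill Quality of Life Questionnaire-E (MQOL-E"), together with the pain and fear-of-death forms, and both repeat all three afterwards.
- **Dependence stated by the authors** (II.A): "The psychological distress of the patient-caregiver dyad is interconnected and highlights the interdependence and responsiveness to distress as a unit".
- **Size** (IV.D.4): "The study will recruit 20+ patient and caregiver dyads from Prisma Health Hospice of the Foothills". The Sample Size entry (IV.D.3) is n/a.

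Neither document mentions a paired test, a mixed model, a dyad term, clustered standard errors or analysis by role. Data Management (IV.E.5) assigns each participant a random individual ID and describes no dyad identifier.

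**The concern.** Two kinds of dependence run through these data. One is the same person measured twice. The other is two people in one pair sharing one session. Pairing pre with post removes the first and leaves one change score per person; those changes may still be correlated within the dyad.

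With a positive correlation, the independence assumption fails in opposite directions depending on the result reported. A mean change pooled over everyone gets a standard error that is too small, so false positives exceed the nominal level. A patient-versus-caregiver comparison gets one that is too large, so real role differences are missed. The aims are worded for dyads and the analysis section mentions both members, so either result could well be reported. The data are also meant to support an application for a larger study, where misjudged precision would carry forward.

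**Working it through.** There is no planned figure to reproduce: the documents give no alpha, power, effect size, SD or correlation.

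**Inputs.** From the documents: m = 20 dyads (the stated minimum), so 40 people, both members measured before and after. Assumed: two-sided 5% level; normal change scores with equal SDs in the two roles; within-dyad correlation of change ρ from 0 to 0.5.

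**Formulas**, for within-person changes:

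- Pooled mean over 2m people: true SE / naive SE = √(1+ρ); effective N = 2m/(1+ρ).
- Patient minus caregiver: true SE / naive SE = √(1−ρ).
- Worked example at ρ = 0.2, pooled: √1.2 = 1.095; 40/1.2 = 33.3; normal approximation to the error 2×[1−Φ(1.96/1.095)] ≈ 7.4%.

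Simulation with the exact t critical values (at least 200,000 trials per setting) gives:

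| ρ | SE ratio, pooled | Effective N | Error, 40 pooled | SE ratio, between roles | Error, independent test between roles |
|---|---|---|---|---|---|
| 0 | 1.00 | 40.0 | 5.0% | 1.00 | 5.0% |
| 0.1 | 1.05 | 36.4 | 6.2% | 0.95 | 3.9% |
| 0.2 | 1.10 | 33.3 | 7.3% | 0.89 | 3.0% |
| 0.3 | 1.14 | 30.8 | 8.5% | 0.84 | 2.1% |
| 0.5 | 1.22 | 26.7 | 11.0% | 0.71 | 0.7% |

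Power for an assumed 0.6 SD difference in change between roles:

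| ρ | Independent-samples test | Paired across the dyad |
|---|---|---|
| 0.2 | 45% | 52% |
| 0.3 | 45% | 58% |
| 0.5 | 44% | 72% |

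**Analyses that are not affected.** A one-sample t-test on each dyad's average change, a paired test across roles, and a within-person paired test in one role alone all hold about 5% error at every ρ tried.

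**The test taken literally.** Suppose 40 pre values are compared with 40 post values as independent groups. With pre/post correlation r (also assumed), true SE / naive SE = √[(1−r)(1+ρ)].

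- r = 0.5, ρ = 0.3: √(0.5×1.3) = 0.81, error about 1.5%.
- r = 0.7, ρ = 0.3: √(0.3×1.3) = 0.62, error about 0.2%.
- r = 0.3, ρ = 0.5: √(0.7×1.5) = 1.02, error about 5.6%.

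The missing pre/post pairing dominates here, and the result is usually conservative.

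**Cost of the correct pooled interval.** The width ratio is √(1+ρ) × t(19 df)/t(39 df), with t values 2.093 and 2.023. At ρ = 0.2: 1.095 × 1.035 = 1.13. At ρ = 0.5: 1.225 × 1.035 = 1.27.

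**The case against.** The strongest reply is that the documents commit to neither affected result. The only contrast that section IV.E.7 spells out is pre versus post. The SAP sentence does not say over whom the means are taken, and the pain outcome is worded for patients only, although the procedures have both members complete the pain form. Analysis by role is a fair reading, and within one role the problem disappears. This stands, and it makes the figures above conditional.

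Three stronger readings are tempting, and the documents do not support them:

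- **That the SAP pools everyone.** It is silent on this; silence is not a pooling plan.
- **That the plan as written inflates false positives.** Inflation needs both within-person pairing and pooling of roles. The literal unpaired test mostly errs the other way.
- **That every dyad-level result is wrong.** One summary per dyad gives a valid test, and the SAP's descriptive means and SDs carry no standard error at all.

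The size is also uncertain. The protocol's statement about interdependence concerns psychological distress; it does not establish correlated pain changes over a 5 to 15 minute session. If caregivers' changes had a quarter of the patients' SD (an assumption), pooled error would be about 6.0% at ρ = 0.2 and 7.8% at ρ = 0.5.

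What the reply does not remove is that the protocol says differences will be tested, names only an independence-based test, and leaves the unit of analysis open in a study built on pairs.

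**Conclusion.** The concern holds in conditional form. Neither document handles patient-caregiver dependence, and neither says whether the roles are pooled, compared or separated. Once pre and post are paired within person, treating 40 people as independent would put pooled type I error at about 6% to 11% for ρ from 0.1 to 0.5. Comparing roles with the independent-samples test would lower error to about 3% to 0.7%, and power for 0.6 SD to about 45% against an attainable 52% to 72%, for ρ from 0.2 to 0.5. At ρ = 0 there is no problem. These sizes rest on 20 complete dyads, normal changes, equal variances and an assumed ρ. This is separate from the missing pre/post pairing in the same sentence of the protocol, and would remain after that was corrected.

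**What to change.** In Protocol IV.E.7 and the SAP, in matching words:

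1. Replace the independent-sample t-tests with within-person change, analysed separately for patients and caregivers.
2. For any pooled or between-role result, make the dyad the unit. With complete pairs, use a one-sample t-test on dyad-average change and a paired t-test across roles. Otherwise fit a mixed model of change with role as a fixed effect and a dyad random intercept, or an unstructured 2×2 covariance; this also keeps dyads with one member missing.
3. State which of these results will be reported for each scale, including whether caregivers' pain scores are analysed.
4. Add a dyad identifier to the de-identified dataset described in IV.E.5. Without it the dyad-level analyses cannot be run.
5. Report the number of dyads alongside the number of people.

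The cost is some wording, one extra data field set up before de-identification, and a few lines of code. The statistical price is a pooled interval about 13% to 27% wider at ρ 0.2 to 0.5 with 20 dyads. If ρ were zero, the loss of degrees of freedom alone would still widen it by about 3.5% (2.093/2.023).
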